# 11.5.2.2 Safety

All safety assessments will take place in the total vaccinated population, according to the treatment received and will be summarized overall and by study site. All subject-level percentages (solicited/unsolicited AEs etc.) will be supplemented with two-sided 95% CIs computed via the Clopper-Pearson method. Summaries will include all events occurring on or after the date of each vaccination. Individual summaries (denominators for percentages) will be limited to the number of subjects within the appropriate analysis population with data available for analysis for the given endpoint.

#### 11.5.2.2.1 Unsolicited Adverse Events

All unsolicited AEs, including serious and/or severe AEs will be coded according to the Medical Dictionary for Regulatory Activities (MedDRA) version 20.1 or later. A summary table will be prepared for unsolicited AEs presenting incidence of any AE, any related AE, any serious AE, any severe AE, any AE of grade  $\geq 2$ , any related AE of grade  $\geq 2$ , and any AE leading to study withdrawal where a subject only contributes once. Additional tabulations among these categories will be presented by severity, where relevant, where a subject only contributes once under the maximum severity event recorded. Summary tables will also be prepared for each of these

categories presenting summaries across System Organ Class (SOC), and across PT within SOC, where again each subject only contributes once per SOC/PT combination, and once per SOC. An additional table will include preferred terms occurring in ≥2 subjects (across group, regardless of seriousness, severity, or relationship), sorted in descending order of incidence. Each of these tables will use the form "n (%) m", where n is the number of subjects with an event, (%) is the percent of subjects experiencing that event, using the number in the total vaccinated population for the specific group as the denominator, and m is the number of events of that type within that group, regardless of the number of subjects from which they originate. Listings will be prepared including each of the categories of unsolicited AEs listed above including the verbatim term, the SOC, PT, type, the date and study day of onset and resolution, as well as the seriousness, severity, causality assessment, actions taken, and the outcome.

# 11.5.2.2.2 Reactogenicity

Reactogenicity will be assessed according to immediate (at least 30 minutes post-vaccination) and delayed reactogenicity (within 8 days post-vaccination), as well as combined after each vaccination. Solicited AEs will be summarized overall, by category (local/systemic), by reaction, and by severity within reaction and within category, and by severity and reaction according to post-vaccination day, where each subject is counted once under the maximum severity of each reaction and/or category, where relevant. Analyses involving severity will include those graded ≥2. Summaries of solicited AEs observed across the solicitation period will be accompanied by a two-sided Fisher exact test p-value for a difference among groups, for both local and systemic events (overall and by reaction), as well as across these events (overall). Reactogenicity events ongoing at 7 days post-vaccination will be listed. Duration of reactogenicity events will be summarized by reaction.

Measured injection site features will be summarized by group and post-vaccination time point, including but not limited to pain, erythema/redness, swelling/induration, abscess and pruritis.

## 11.5.2.2.3 Vital Signs

Vital signs, including change from pre-vaccination baseline for post-vaccination visits/time points, will be summarized by parameter and time point. A listing of all vital signs will be produced, which includes the study day, value, units, and change from baseline.

## 11.5.2.2.4 Physical Exam

Baseline (full) physical examination results will be listed, as well as summarized as categorical descriptive statistics, where each subject is only counted once per category. Post-baseline physical examination abnormalities will be summarized by category, and a separate listing will be provided.

## 11.5.3 Analysis of exploratory objective/s

The durability of a single dose of HPV vaccine compared to the two-dose regimen will be explored via utilization of kinetic modeling.

Additional exploratory analyses will include comparisons of GMTs, GMCs, and seroconversion rates following a single dose at 6, 12, and 24 months of Cecolin® compared to a single dose of Gardasil® at 6 months. Similarly, a single dose of Gardasil® and Cecolin® will be compared at 24 months by comparing the 0, 24 Cecolin® and 0,24 Gardasil® and Cecolin® arms prior to the second

vaccination. Finally, the single and two-dose regimens of Cecolin® and Gardasil® in this trial will be compared with rates observed at corresponding time points in recent or ongoing trials of Gardasil® and Cervarix®.

# 11.6 Handling of Dropouts and Missing Data

Missing immunogenicity data will not be imputed and will be analyzed as if they were missing at random. Over the study period, the frequency and percentage of subjects who discontinue from the study will be provided by treatment group. All subjects who discontinue post-randomization will be further described regarding their time to and their reasons for discontinuation. For subjects who discontinue from the study, their data collected before discontinuation will be analyzed under the analysis populations as applicable.

# 11.7 Interim Analysis

Upon collection, shipment, and laboratory analysis of the Month 7 serology sample from the subjects in the 0,6 Cecolin and Gardasil arms, an interim analysis will be initiated. The interim analysis will include the analysis of the primary and secondary immunogenicity endpoints and the analysis of the secondary safety endpoints. Only the sponsor will receive the report, and will receive tables only, without listings. Additional detail will be provided in the SAP.

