6.2. Timing of Analyses

Safety data of each study arm will be prepared and reviewed by the Protocol Safety Review Team (PSRT) and the Data and Safety Monitoring Board (DSMB). For details, refer to Section 6.6.2 and Section 6.6.3.

Upon collection, shipment, and laboratory analysis of the Month 7 serology sample from the subjects in the 0,6 Cecolin and Gardasil arms, an interim analysis will be initiated. The interim analysis will include, for groups 1 and 4, the analysis of the primary and secondary immunogenicity endpoints and the analysis of the secondary safety endpoints for these two groups. Only the sponsor will receive the report generated by Emmes, and will receive a selection of tables and listings (See section 6.6.1).

A final analysis of all data collected will be performed after all data queries have been resolved and the data base locked.

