6.3.3. Per Protocol Population

All participants in the total vaccinated population with no major protocol deviations that are determined to potentially interfere with the immunogenicity assessment of the study vaccine for the relevant time point, were seronegative for the relevant HPV type at baseline, and have a valid serology result for the relevant time point. This population will serve as the primary analysis population for the immunogenicity endpoints. The population will be adapted by time point to include all eligible subjects' data up to the time of the disqualifying protocol deviation.

The criteria for exclusion of participants from the Per Protocol Population will be based on the review of protocol deviations at a Data Review Meeting (DRM) attended by the sponsor, investigator, and CRO representatives.

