6.6. Interim Analysis and Data Monitoring

6.6.1. Interim Analysis

Upon collection, shipment, and laboratory analysis of the Month 7 serology sample from the subjects in the 0, 6 Cecolin[®] and Gardasil[®] arms (i.e., vaccination groups 1 and 4), an interim analysis will be initiated. The interim analysis will include the analysis of the primary and secondary immunogenicity endpoints for groups 1 and 4 and the analysis of all available secondary safety endpoints for these two groups. A DRM will assess protocol deviations for groups 1 and 4 up to month 7. Only the sponsor will receive the report generated by Emmes, and will receive the following tables, figures, and listings:

• Tables 3-16, 18-23, 26-29, 31-38, 46-51, 55-63, 65-67, 74-77, 79-81 83-106, Figures 9-12, and Listings 8, 10, 11, 15, 20, 21.

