8. IMMUNOGENICITY EVALUATION

The primary immunogenicity assessments will be assessed using the per protocol population. Supplementary analyses will be conducted in the total vaccinated population. For all immunological assays with predefined limits of quantitation, percentiles, and bootstrap based confidence intervals (CIs) which achieve the LLOQ or ULOQ will be replaced with "<LLOQ" or ">ULOQ", as appropriate. Analysis of immunological assays will be supplemented by reverse cumulative distribution (RCD) curves with each group for a given visit displayed on the same plot, with different panels for different visits. Assay values <LLOQ will be replaced by LLOQ/2 and values achieving the ULOQ will use the ULOQ as the observed data point in each analysis, except in analyses incorporating left and/or right censoring, in which case all values <LLOQ or >ULOQ will be censored at LLOQ and ULOQ, respectively.

GMC/T, GMC/T ratio, and corresponding confidence limits of the log-scale coefficients will be calculated using SAS PROC GLM with the LSMEANS statement of the log-scale coefficients which will be back-transformed in order to compute the estimate and corresponding confidence limits on the original scale. All models will use the log-transformed concentrations as the dependent variable, treatment group as the explanatory variable, and trial center as a covariate. All GMC/T ratios will be computed using the Cecolin containing arm as the numerator.

The GMC/T ratio and corresponding two-sided 98.3% CI for each comparison will be computed separately for each comparison to Gardasil® 0,6. Sensitivity analyses will be performed for application in the total vaccinated cohort utilizing SAS PROC LIFEREG, incorporating censoring where appropriate at LLOQ and ULOQ, and a Normal error distribution on the log scale, and adjustment for baseline concertation or titer on the log scale if 10% or more observations are censored.

A listing of all immunogenicity results is provided in Listing 10 and Listing 11.

8.1. **Primary Immunogenicity Analysis**

The primary objective of this study is to demonstrate the non-inferiority of Cecolin® administered on 0, 6-month; 0, 12-month; and 0, 24-month two-dose regimens, to Gardasil® using a 0, 6-month two-dose regimen, based on HPV Immunoglobulin G (IgG) antibody levels measured one month after the last dose for HPV types 16 and 18. Non-inferiority will be achieved if the lower bound of the 98.3% CI for the GMC ratio is > 0.5.

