Correlation between neutralizing antibody titers measured by PBNA and IgG antibody concentrations measured by ELISA will be summarized on the continuous scale for anti-HPV 16 and 18 and the following three categories Cecolin only, Gardasil only, and the mixed arm with colors identify timepoints (Figure 7 and Figure 8). The Spearman correlation between ELISA and PBNA results will be computed by type and for Cecolin only, Gardasil only, and the mixed arm. Summaries will be provided by three categories Cecolin only, Gardasil only, and the mixed arm and HPV type (Table 39).

Analysis of immunological assays will be supplemented by reverse cumulative distribution (RCD) curves for each treatment group for a given visit displayed on the same plot, and different panels for different visit (Figure 9 through Figure 12). Log concentration/titer will be on the x-axis and cumulative percent will be on the y-axis.

The analyses for GMC/T and GMC/T ratio will be repeated as a sensitivity analyses based on the total vaccinated cohort utilizing SAS PROC LIFEREG (Table 42 through Table 45).

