12. SUMMARY OF CHANGES IN THE CONDUCT OF THE STUDY OR PLANNED ANALYSES

An additional exploratory analysis has been added (not included in version 1.6 of the protocol) where the antibody kinetics model will be implemented.

A listing of all pre- and post-vaccination vital signs, including change from baseline, will be included but no summary tables will be presented, as they are not considered to be medically relevant in a stage 3 study.

Extra versions of Tables 84 and 87 will be generated that will include all SAEs and all unsolicited AEs rather than only those within one month (30 days) of each dose. These 2 tables (Tables 89 and 97) will be submitted to ClinicalTrials.Gov.

13. **REFERENCES**

Not applicable.

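### SAP 6.2 and 6.6.1 give the sponsor listings at the interim, including all immunogenicity results, although Protocol 11.7 allows none and SAP 12 does not record the change

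*Protocol*

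**What the plan says.** Protocol 11.7 starts an interim analysis once the Month 7 samples from the two 0,6-month arms (Groups 1 and 4) have been tested. On who sees what, it says: "Only the sponsor will receive the report, and will receive tables only, without listings". It leaves further detail to the SAP.

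SAP 6.2 says the sponsor "will receive a selection of tables and listings" and refers to section 6.6.1. That section gives a list of tables followed by "Figures 9-12, and Listings 8, 10, 11, 15, 20, 21". SAP 8 explains two of these items: "A listing of all immunogenicity results is provided in Listing 10 and Listing 11".

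On per-protocol membership, SAP 6.6.1 adds: "A DRM will assess protocol deviations for groups 1 and 4 up to month 7". SAP 6.3.3 bases exclusions on "review of protocol deviations at a Data Review Meeting (DRM) attended by the sponsor, investigator, and CRO representatives". SAP 7.2 says that a deviation need not lead to exclusion.

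SAP 12 is where departures from the protocol are logged. Its first entry reads: "An additional exploratory analysis has been added (not included in version 1.6 of the protocol". The other two entries cover vital-sign summaries and extra adverse-event tables.

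**The concern.** The two documents give opposite instructions for the same report. The protocol excludes listings, and the SAP names six. The SAP may add detail where the protocol asks for it, but releasing listings reverses an express limit. Nothing in SAP 12 shows that the reversal was deliberate.

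Listings 10 and 11 are the ones that matter. They would put individual antibody results in the hands of a party that also takes part in judging per-protocol exclusions. Group 4 at Month 7 is the control for all three co-primary ratios and for the mixed-regimen ratio. If a deviation up to Month 7 came to light, or was reopened, after the interim, someone who had seen that girl's result could help decide whether she stays in. Excluding a Group 4 girl would move every remaining ratio against that control in the same direction.

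**Working it through.** No power or alpha figure is involved. The check is a comparison of the texts, a count and a timeline.

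**Content of the interim report**

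| Source | Tables | Listings | Figures |
|---|---|---|---|
| Protocol 11.7 | yes | excluded | not mentioned |
| SAP 6.2 | yes | yes | not mentioned |
| SAP 6.6.1 | yes | 8, 10, 11, 15, 20, 21 (six) | 9 to 12 (four) |

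**What the items are**

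- Listings 10 and 11: all immunogenicity results (SAP 8). SAP 6.2 and 6.6.1 confine the interim analysis to Groups 1 and 4, so the interim versions presumably cover those groups. The SAP does not say so for the listings, and their shells were not in the text available.
- Listing 8: non-study vaccines (SAP 7.3.2). Listing 15: deaths, SAEs and other significant events (SAP 9.2). Listing 20: medications given after an SAE (SAP 7.3.2). Listing 21: pregnancies (SAP 9.3).
- Figures 9 to 12: reverse cumulative distribution curves by group and visit (SAP 8.2), so group-level.

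**Is the change recorded?** SAP 12 has three entries. None concerns the interim report.

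**Which comparisons are still open at the interim?** The days come from the visit schedule (Protocol 6.2.7, 6.2.11, 6.2.14), ignoring visit windows.

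- For girls enrolled on the same day, Group 2's post-dose-2 sample falls 395 − 210 = 185 days after Group 4's, and that of Groups 3 and 5 falls 760 − 210 = 550 days after.
- Enrolment takes 5 to 6 months (Protocol summary, Study Duration), or about 150 to 180 days at 30 days a month. The last Group 4 Month 7 sample therefore falls about 150 + 210 = 360 to 180 + 210 = 390 days after the first enrolment.
- The first Group 2 sample is due on day 395, which is 5 to 35 days after that last Group 4 sample. Allowing for shipment and testing, some Group 2 samples may already be in when the interim report is released.
- The first Group 3 and 5 samples are due on day 760, which is 370 to 400 days after it. The 0,24-month primary comparison and the mixed-regimen comparison are thus still open unless shipment and testing take more than a year.

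**What already limits the risk**

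- The interim package includes per-protocol tables (21 to 23, and the primary results in 26 to 29), so in practice the interim Data Review Meeting must come before release.
- SAP 6.3.3 keeps a participant's data up to the time of a disqualifying deviation.
- Per-protocol counts by group and visit (Tables 4, 7 and 10) and Group 4 results (Tables 26 and 29) are in the interim package and are also planned final outputs, so a later change would be visible.
- Protocol 11.5.1.1 and SAP 8 and 8.1 plan analyses in the total vaccinated population, from which the meeting cannot remove anyone.

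**What is left open.** Neither document says that the interim Month 7 decisions for Groups 1 and 4 carry forward to the final analysis, or that the meeting works without sight of antibody values.

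**The case against.** The strongest reply accepts the textual mismatch and disputes everything built on it. The trial is open-label, and the CRO runs the analyses under the sponsor's responsibility (Protocol 11.5). The protocol gives no reason for excluding listings and does not otherwise keep serology from the sponsor, so deleting two listings creates no firewall. This stands: reading the sentence as protection for the exclusion decisions is an inference. It limits the size of the point but does not remove the contradiction.

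The scope can also be narrowed. Figures 9 to 12 appear only in SAP 6.6.1, they show group-level curves of a kind Protocol 11.5 foresees, and the protocol's contrast is most naturally between summaries and subject-level data. The sponsor's medical officer already reviews SAEs as they occur, so Listings 15 and 20 tell the sponsor little that is new. Both remarks are fair. These items need reconciling on paper, but they are not where any risk lies.

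Amending Protocol 11.7 would cure the mismatch for Listings 10 and 11 as well. That is true. Removing them is a preference, which rests on the sponsor's seat at the exclusion meeting.

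Finally, a hard freeze of Month 7 membership could keep a girl whose genuine major deviation is found later, contrary to the per-protocol definition in Protocol 11.4.3 and SAP 6.3.3. This stands too, and the fix below avoids a freeze.

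**Conclusion.** The contradiction is explicit: six listings are named where the protocol excludes listings, two of them hold all immunogenicity results, and SAP 12 is silent. It is a minor inconsistency with a nearly free remedy.

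A reader might infer that the interim release inflates the type I error or breaks a sponsor firewall. The documents support neither. Protocol 11.7 and SAP 6.6.1 state no decision rule for the interim, the trial is open-label, and no firewall is described. Any effect would need a deviation that is arguable, surfaces after the interim and is then judged with knowledge of the titre. The documents give no rate for such cases, so no error rate can be put on them. The effect is likely small, because the total vaccinated analyses and the repeated Group 4 tables would tend to expose selective exclusion.

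Confidence is high for the mismatch itself. The link to per-protocol exclusions is a reasoned inference.

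**What to change.** 1. Bring SAP 6.2 and 6.6.1 into line with Protocol 11.7, preferably by removing Listings 10 and 11 from the interim package.
2. For any listing or figure that is kept, amend Protocol 11.7 and record the change, with its reason, in SAP 12.
3. State in SAP 6.3.3 that the Data Review Meeting judges deviations without sight of post-vaccination antibody values. Baseline serostatus and availability of a valid result can be applied by program, so the meeting does not need those values.
4. State in SAP 6.6.1 that the interim Month 7 decisions for Groups 1 and 4 are documented and carried forward. Deviations discovered later are judged in the same way, without antibody values, and any resulting change is recorded as a change from the interim.

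The cost is SAP wording, plus a short protocol amendment if any of the listings or figures stay. Design, sample size and participant procedures are untouched. The downside is that the sponsor waits until the final analysis for subject-level serology.

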# 12 QUALITY ASSURANCE AND QUALITY CONTROL

Guidance on internal and external processes to assure effective protocol implementation, quality of the research conducted and compliance with sponsor and applicable regulatory requirements

#### 12.1 General Considerations

The study will be conducted in full compliance with the protocol and ICH GCP to provide public assurance that the rights, safety, and well-being of trial participants are protected, and that the clinical trial data are credible. To ensure quality and standardization, the site will develop Standard Operating Procedures (SOPs) for key protocol procedures and conduct the study guided by the study Manual of Procedures or other written guidelines. The sites will also develop routine operational checks to verify that critical protocol requirements and procedures are executed correctly and completely at the time the work is being performed. Prior to the initiation of the study, the Sponsor and/or the CRO delegated by the Sponsor will conduct training on the protocol, including applicable SOPs, for all study staff.

The investigational sites will provide direct access to all trial related clinics, source data/documents, and reports for the purpose of monitoring and auditing by the sponsor, and inspection by local and regulatory authorities.

#### 12.2 External Monitoring

PATH, the sponsor of this study is responsible for ensuring that the study is conducted in accordance with ICH GCP and regulatory requirements. For this purpose, monitors under contract from the Sponsor will provide external monitoring for this study. A site initiation visit will be conducted prior to beginning the study, and monitoring will be conducted at initiation, during, and at closeout of the study. During the study, monitors will visit the clinical site at intervals to verify compliance to the protocol; completeness, accuracy, and consistency of the data and study product

accountability; adherence to ICH GCP and applicable regulations. As needed and when appropriate, the monitors will also provide clarifications, additional training to help the site resolve issues identified during the monitoring visit. As appropriate and informed by risk assessment, remote centralized monitoring activities may be considered in place of or to supplement onsite monitoring. These may include analysis of data quality (e.g. missing or inconsistent data, outlier data), identify data trend not easily detected by onsite monitoring and performance metrics (e.g., screening or withdrawal rates, eligibility deviations, timeliness and accuracy of data submission).

The extent and frequencies of the monitoring visits will be described in a separate Study Monitoring Plan developed prior to study initiation. The investigator will be notified in advance of the scheduled monitoring visit. The monitor should have access to all trial related sites, participant medical records, study product accountability and other study-related records needed to conduct monitoring activities. The Sponsor will share the findings of the monitoring visit, including any corrective actions, with the site investigator. The site PI and the monitor must agree to cooperate to ensure that any problems detected in the course of these monitoring visits are resolved in a predefined timeframe.

